# **Secondary Objectives:**

- To compare the number of hospitalizations related to SREs between standard of care and upfront RT arms
- To compare pain-related quality of life of between standard of care and RT arms, using the Brief Pain Inventory (BPI form
- To collect health care utilities in the standard of care and RT arms using the EuroQol Group EQ-5D-5L form
- To compare pain-free survival (PFS) and overall survival (OS) between RT and standard of care arms.
- To evaluate CTCAE v4 toxicity events in the upfront RT arms.

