## **4.2.4 EuroQol**, **EQ-5D-5L**

Patients enrolled on either arm will undergo assessment of patient reported health utilities using the EuroQol EQ-5D-5L questionnaire at baseline, 3 months, 6 months, 12 months, and optionally but recommended within one week of any SRE (Appendix, ~10 minutes to complete). For patients randomized to receive upfront, early RT, they will complete the form prior to RT. It is a standardized instrument created by the EuroQol Group as a measure of health utility. It is a generic global quality of life measurement tool. It consists of a descriptive system that includes 5 dimensions (5D, each measured by a single item) (mobility, self-care, usual activities, pain/discomfort, and anxiety/depression) each of which can be assessed on 5 levels (5L) (no problems, slight problems, moderate problems, severe problems, and extreme problems). Respondents are asked to indicate which response option best describes their health "today".

Respondents are asked to indicate their health state by marking the box associated with the most appropriate statement in each of the 5 dimensions, resulting in a one digit number expressing the level selected for that dimension (1-5 from no problems to extreme problems, note these do not carry numeric value and should not be summarized as such)

- The digits for the 5 dimensions are then combined into a 5-digit code describing the respondent overall health state

Page **11** of **30** Version: 2/26/16

- The 5-digit health states are then transformed to overall index values (sometimes called preference values, utilities, or QALY weights) based on country-specific value sets provided by the EuroQol Group. The United States value set will be used to obtain the overall index values and are available at http://www.euroqol.org/about-eq-5d/valuation-of-eq-5d/eq-5d-5l-value-sets.html for the current study. The index value has interpretive anchors at 0 (dead) and 1 (best possible health).

- In order to minimize missing values on the overall index value, missing values are given a numeric value of 9; ambiguous values (i.e. two responses to the same question) are also given a numeric value of 9 and are accounted for in the published overall index values.

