Palliative radiation therapy is a well-established, frequently used treatment for patients with metastatic disease. It is often the standard of care for patients with symptomatic metastatic lesion. It is extremely unlikely to be more toxic or cause earlier deaths.

We expect to enroll all 74 patients within 2 years.

Secondary objectives will be analyzed per patient. Unless otherwise specified, all endpoints are defined within the time window from the date of randomization to death or 12 months, whichever occurs first.

To compare the number of hospitalizations related to SREs between standard of care and upfront, early palliative RT arms we will employ a Wilcoxon rank sum test.

To compare quality of life between standard of care and RT arms, using the Brief Pain Inventory (BPI) and EuroQol Group EQ-5D-5L forms, we will test the difference (between the two arms) of the survey results at the following time points: 3 months, 6 months, 12 months and optionally but recommended within one week of any SRE. The individual quantitative scores derived from the BPI, and the utility scores as well as the overall health scores derived from EQ-5D-5L, will be summarized at these assessment times using descriptive statistics (means and standard deviations, medians and quartiles). Differences between the two arms in terms of these quantitative scores at various time points of interest will be evaluated for both statistical and clinical significance using Wilcoxon rank

Page **22** of **30** Version: 2/26/16

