sum tests and established minimally important differences (MIDs) for the various measures, respectively. For scale scores with no established MIDs, the "half standard deviation" rule will be applied (i.e., differences of a half standard deviation will be considered clinically significant). At the conclusion of the study data at each time point will be presented, the number of patients in each group at a given time point will be documented, and the mean EQ-5D-5L and BPI scores for each group will be plotted over time and longitudinal pattern will be examined with the possibility of proposing more complicated regression methods such as the linear mixed models. The categorical answers (e.g., YES vs NO) from EQ-5D-5L will be compared between the two arms using Fisher"s test at each time point as well and odds ratios together with confidence intervals will be computed. Other non-quantifiable answers (e.g., treatment receiving for pain) will be summarized descriptively. For the last question in BPI, the score for pain interference on the BPI Short Form is the mean of the 7 interference questions as long as at least 4 are completed.

For comparing pain-free survival and overall survival between the two arms, both of which are time to event endpoint (time from randomization to start of opioids or death which is not necessarily within 12 months from randomization), we will use log-rank test.

To evaluate CTCAE v4 toxicity events in the upfront RT arms, we will tabulate all toxicities and summarize the CTCAE v4.03 scores and present descriptive statistics. This will be done at 3 months, 6 months, and 12 months from randomization.

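### Section 14 plans Fisher's tests and odds ratios for YES/NO answers from EQ-5D-5L, but its items as described have five ordered levels, and no cut-point or ordinal method is named

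*Combined protocol and SAP*

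**What the plan says.** Section 4.2.4 describes EQ-5D-5L as five dimensions, "each of which can be assessed on 5 levels (5L) (no problems, slight problems, moderate problems, severe problems, and extreme problems". The level chosen is recorded as a digit from 1 to 5, with the caution "note these do not carry numeric value and should not be summarized as such". The five digits form a health state that is converted to an index value. The section mentions no item answered yes or no.

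Section 14 plans two layers of EQ-5D-5L analysis.

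- **Scores.** It takes "the utility scores as well as the overall health scores derived from EQ-5D-5L", summarises them descriptively, and has arm differences "evaluated for both statistical and clinical significance using Wilcoxon rank" sum tests and minimally important differences respectively. Plots over time and possible mixed models follow.
- **Items.** It then states that "The categorical answers (e.g., YES vs NO) from EQ-5D-5L will be compared between the two arms". The method named for this comparison is Fisher's test, repeated at every assessment and accompanied by odds ratios with confidence intervals.

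No text says how five levels become two, or which odds ratio is meant. The corresponding secondary objective is modest: "To collect health care utilities in the standard of care and RT arms using the EuroQol Group EQ-5D-5L form".

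**The concern.** The item-level sentence describes data that the instrument, as set out in Section 4.2.4, does not produce. The analyst can fill the gap in two ways, and each has a problem.

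- **Keep all five levels.** Fisher's test extends to a 2 x 5 table, but it treats the levels as unordered and leaves no single odds ratio to report.
- **Split into two.** This gives a 2 x 2 table and an odds ratio, but five levels allow four cuts and none is named. The choice could be made after seeing the data, and differently for each of 5 dimensions x 3 time points = 15 comparisons.

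What is at stake is the interpretability of the dimension-level results: an odds ratio whose definition was open, and possibly lower power in a small trial.

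**Working it through.** **Is there a plan figure to reproduce?** Not for EQ-5D-5L, where Section 14 gives no effect size, alpha, sidedness or power. Its only power statement concerns the primary endpoint (60% v 30%, one-sided 5%, power above 80%), and that reproduces:

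n per arm = [1.645 x sqrt(2 x 0.45 x 0.55) + 0.842 x sqrt(0.6 x 0.4 + 0.3 x 0.7)]^2 / 0.30^2 = (1.157 + 0.565)^2 / 0.09 = 33, or 66 in total; 66 / 0.9 = 73.3, so 74.

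Here it serves only to set a realistic number per arm.

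**Patients available.** Section 14 expects one-year follow-up in 60-80% of enrolled patients. With 74 / 2 = 37 per arm, that is 0.60 x 37 = 22 to 0.80 x 37 = 30 per arm at 12 months.

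**Assumptions (not in the documents).** Level shares in the standard-of-care arm of 30/30/20/15/5% from no to extreme problems; 30 per arm; two-sided 5%; a common odds ratio of 3 across all cuts. The shifted shares follow from the cumulative odds:

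- cumulative shares 0.30, 0.60, 0.80, 0.95 have odds 0.429, 1.5, 4, 19
- multiplied by 3: 1.286, 4.5, 12, 57
- back to cumulative shares: 0.563, 0.818, 0.923, 0.983
- shares in the RT arm: about 56/26/10/6/2%

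**Simulated power, 30 per arm.** The unordered test is a permutation chi-square on the 2 x 5 table, standing in for Fisher's test on that table.

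| Common odds ratio | Rank test (ordered) | Unordered 2 x 5 | Fisher on a split, by cut |
|---|---|---|---|
| 2.5 | 46% | 28% | - |
| 3 | 61% | 43% | under 1% to 45% |

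Repeat runs move these by two or three percentage points.

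**Sensitivity to the assumed shares, common odds ratio 3.**

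| Assumed shares | Per arm | Rank test | Fisher on a split |
|---|---|---|---|
| 20/20/20/20/20% | 33 | 69% | 17-54% by cut |
| 40/30/20/8/2% | 33 | 63% | 0-54% by cut |
| 70/20/7/2/1% | 33 | 41% | 0-30% by cut |
| the same three | 20 | 47%, 42%, 26% | best cut 27%, 27%, 17% |

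**Other effect patterns.**

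- Shares of 30/25/20/15/10% become 65/5/5/15/10%, so the effect lies only between no and any problems (33 per arm): Fisher at that cut 78%, rank test 49%.
- Shares of 30/30/20/15/5% become 58/2/20/15/5%, so patients move only from slight to no problems (30 per arm): unordered test 81%, Fisher at no v any problems 49%, rank test 22%.
- No problems rises from 30% to 65% and the other levels shrink in proportion (30 per arm): Fisher at that cut 70%, rank test 69%.

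**Open cut and false positives.** With no true effect and 30 per arm, a single fixed cut gives about 3% false positives, because Fisher's test is conservative. If any of the four cuts may be reported, the rate is about 6-8% per dimension and time point.

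**The case against.** The strongest reply is that this is an added analysis with loose wording. YES/NO is offered only as an example. The utility index draws on all five levels of all five dimensions and is compared by a rank test, so the graded information is used. Treating the levels as categories is consistent with the warning that the digits carry no numeric value. Fisher's test is also a reasonable choice with 22 to 30 patients per arm at 12 months and sparse upper levels.

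Much of this stands, and it rules out three stronger readings that a reader might infer.

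- **That the analysis cannot be run.** It can, on a 2 x 5 table or after a split. What is missing is the cut or the model that defines the odds ratio.
- **That the plan loses power.** The documents give no level distribution, effect size or power for EQ-5D-5L. The loss appears under a common shift, and the other patterns above show it vanishing or reversing.
- **That the whole EQ-5D-5L analysis is misfitted.** The score comparisons are unaffected.

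The reply does not remove the core point. An example that matches none of the described items gives the analyst no rule. The advantage of Fisher's test at one particular cut can be claimed properly only if that cut was fixed beforehand. The caution about numeric value does not argue against ordinal methods, which use only the order of the levels.

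**Conclusion.** The mismatch between Sections 4.2.4 and 14 is real and rests on the text alone. The instrument as described has five ordered levels and no yes/no item, while the plan promises Fisher's tests and odds ratios without a cut or an ordinal model. It is minor: it touches one supplementary analysis of a secondary outcome and does not affect the primary endpoint or the sample size.

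Its effect on power is conditional. Under a common odds ratio of 3, with the assumed 30/30/20/15/5% shares and 30 per arm, the ordered test gains 61 - 43 = 18 points over the unordered test and 61 - 45 = 16 points over Fisher at the best cut, with far larger gains over a poor cut. If the effect is confined to one cut, the gain can disappear or change sign. Leaving the cut open also lets the false-positive rate rise above 5% if the cut is picked on the results.

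**What to change.** Replace the item-level sentence in Section 14 with wording to this effect: for each EQ-5D-5L dimension, the five levels will be compared between arms at 3, 6 and 12 months by the Wilcoxon rank sum test, and the common odds ratio with its confidence interval will be reported from a proportional-odds model. If a two-level summary is also wanted, name one cut in advance for all dimensions and time points (for example no problems v any problems) and apply Fisher's test to that.

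The cost is one or two sentences, with no new data and no change in sample size. There are two downsides. The common odds ratio relies on the proportional-odds assumption. An ordinal test can also be less powerful than Fisher's test if the true effect is confined to a single cut, and a cut named in advance would partly guard against that.

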# Less likely

- Hematologic: decrease in blood counts leading to infection
- Genitourinary: bladder irritation

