# 11.1 Adverse Event Reporting

This study will use the Common Terminology Criteria for Adverse Events (CTCAE) version v4.03 for adverse event (AE) reporting. After informed consent is signed, study site personnel will record the occurrence and nature of each patient"s pre-existing conditions, including clinically significant signs and symptoms of the disease. During the study, site personnel will record any change in the pre-existing condition(s), and the occurrence and nature of any new adverse events.

All AEs related to protocol procedures are reported. All AEs occurring after the patient receives the first dose of radiation therapy must be reported in regard to their assessment of the potential relatedness of each AE to protocol procedure, studied disease state, and/or radiation modality via CRF. If a patient sradiation treatment is discontinued as a result of an AE, personnel must clearly report the circumstances and data leading to any dosage reduction or discontinuation of treatment.

Events leading to the clinical outcome of death due to disease progression will be included as part of the safety and efficacy analyses for this study.

If a death is considered related to treatment, the death should be reported as a Serious Adverse Event and appropriate guidelines followed for SAE reporting. Any clinically significant findings from labs, vital sign measurements, and other procedures should be reported as well.

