## 11.2 Definitions of Adverse Events

#### 11.2.1 Adverse Event (AE)

Defined as any harm or untoward medical occurrence in a research participant administered a medical product, medical treatment or, procedure even if it does not necessarily have a causal relationship with the product, treatment, or procedure. An adverse event can be any unfavorable and unintended sign (including an abnormal laboratory finding, for example), symptom, or disease temporally associated with the use of a medical product, medical treatment, or procedure, whether or not considered to be related. Resources containing information on AEs include monthly transcripts, assessment forms obtained after each clinic visit, and hospital progress and discharge notes. Grade ≥3 adverse events other than hematologic toxicities will be recorded, graded, and reported appropriately.

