# 11.2.4 Attribution to Radiation Therapy

For reporting purposes, attribution is the assessment of the likelihood that an adverse event is caused by the research agent, or protocol intervention. The attribution is assigned by the principal investigator after considering the clinical information, the medical history of the subject, and the past experience with the research agent/intervention.

This is recorded using one of the following five categories:

- Unrelated
- Unlikely Related
- Probably Related
- Possibility Related
- Definitely Related

Related events are those which are most certainly caused by the procedures involved in the research.

Possibly related events are those which may have been caused by the procedures involved in the research.

Not related events are those which are due to an underlying disease, disorder, or condition of the subject, or due to other circumstances unrelated to the research or any underlying disease, disorder, or condition of the subject.

Unknown events are those which have an unclear relationship to the procedures involved in the research, both because more information is needed, and will be provided in follow-up, or because there is no way to make a determination.

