## 17.2 Serious Adverse Event (SAE) Reporting

An adverse event is considered serious if it results in ANY of the following outcomes:

- Death
- A life-threatening adverse event
- An adverse event that results in inpatient hospitalization or prolongation of existing hospitalization
- A persistent or significant incapacity or substantial disruption of the ability to conduct normal life functions
- A congenital anomaly/birth defect
- Important Medical Events (IME) that may not result in death, be life threatening, or require hospitalization may be considered serious when, based upon medical judgment, they may jeopardize the patient or participant and may require medical or surgical intervention to prevent one of the outcomes listed in this definition

Note: Hospital admission for a planned procedure/disease treatment is not considered an SAE.

Page **26** of **30** Version: 2/26/16

SAE reporting is required as soon as the participant starts investigational treatment/intervention. SAE reporting is required for 30-days after the participant"s last investigational treatment/intervention. Any events that occur after the 30-day period that is unexpected and at least possibly related to protocol treatment must be reported.

Page **27** of **30** Version: 2/26/16

Please note: Any SAE that occurs prior to the start of investigational treatment/intervention and is related to a screening test or procedure (i.e., a screening biopsy) must be reported.

All SAEs must be submitted in PIMS. If an SAE requires submission to the HRPP office per IRB SOP RR-408 'Reporting of Serious Adverse Events', the SAE report must be submitted within 5 calendar days of the event, All other SAEs must be submitted within 30 calendar days of the event.

The report should contain the following information:

- The date the adverse event occurred
- The adverse event
- The grade of the event
- Relationship of the adverse event to the treatment(s)
- If the AE was expected
- Detailed text that includes the following
  - An explanation of how the AE was handled
  - o A description of the participant's condition
  - Indication if the participant remains on the study
- If an amendment will need to be made to the protocol and/or consent form
- If the SAE is an Unanticipated Problem

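### Section 11.2.1 limits recording to Grade ≥3 non-haematologic adverse events, which conflicts with Sections 11.1, 11.3 and 14 and could leave gaps in the RT-arm toxicity table

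*Combined protocol and SAP*

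**What the plan says.** - **Objective (Section 2.0).** Toxicity is a secondary objective for the radiation arm alone: "To evaluate CTCAE v4 toxicity events in the upfront RT arms".
- **Analysis (Section 14.0).** "To evaluate CTCAE v4 toxicity events in the upfront RT arms, we will tabulate all toxicities and summarize the CTCAE v4.03 scores". The summary is descriptive, at months 3, 6 and 12.
- **Narrow recording rule (Section 11.2.1).** "Grade ≥3 adverse events other than hematologic toxicities will be recorded, graded, and reported appropriately".
- **Broad recording rule (Section 11.1).** "All AEs occurring after the patient receives the first dose of radiation therapy must be reported", by way of the case report form. The same section adds: "Any clinically significant findings from labs, vital sign measurements, and other procedures should be reported as well".
- **Follow-up of events (Section 11.3).** Site staff track any adverse event throughout the study and enter its highest grade on the case report form. There is no grade threshold and no haematologic exception.
- **Doubtful attribution (Section 11.2.2).** Where relatedness is in question, events of Grade 3 or above go to the principal investigator and the IRB, again without a haematologic exception.
- **Listed harm (Section 11.0).** Among the less likely effects, for both abdomen/pelvis and spine: "Hematologic: decrease in blood counts leading to infection".

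**The concern.** A table of all toxicities is only as complete as the rule that feeds it, and here two rules give different contents. The category that Section 11.2.1 excepts is not incidental. Lowered blood counts are part of a risk that the protocol itself names for spine and pelvic fields. Junctional spine, hip and sacroiliac disease are among the lesions to be irradiated, at up to five sites per patient.

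The participants have few or no symptoms from these lesions, so the tolerability of treating early is part of what the trial should report. If staff work from Section 11.2.1, the published table could show few or no cytopenias, and little low-grade toxicity, because they were not recorded. A reader could not tell that from a true absence. If different staff follow different rules, the table mixes the two.

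**Working it through.** No arithmetic applies: the point asserts no figure, and the documents give no haematologic event rates. The check is to ask, for each class of Arm 2 event after the first radiation dose, what each rule does with it.

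| Event in Arm 2 | Section 11.2.1 | Sections 11.1 and 11.3 | Expected in the Section 14 table |
|---|---|---|---|
| Grade 1–2, non-haematologic | Below the threshold: left out | Recorded | Yes |
| Grade 1–2 cytopenia | Below the threshold and excepted: left out | Recorded | Yes |
| Grade ≥3 cytopenia | Excepted: left out | Recorded | Yes |
| Grade ≥3 infection after cytopenia | Recorded | Recorded | Yes |

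1. The first three rows disagree and the last agrees. The conflict is therefore wider than haematology, because the grade threshold in Section 11.2.1 is also at odds with the other sections.
2. The listed harm is compound: a fall in counts that leads to infection. Under the narrow rule the severe infection survives and the cytopenia behind it does not. An infection that leads to admission also meets the SAE definition in Section 17.2: "An adverse event that results in inpatient hospitalization or prolongation of existing hospitalization".
3. Most of the text favours capture. Sections 11.1, 11.3 and 14 all point that way, as does Section 11.2.2 for Grade 3 or above with doubtful attribution. Section 10 also has Arm 2 assessed by CTCAE every five treatment days without a grade threshold. Section 11.2.1 stands alone on the other side.
4. No section says which rule governs. The appendices listed in Section 20.0 are the pain inventory, the EQ-5D-5L and the lesion worksheet, and none of these is an adverse-event form that would settle it.
5. Size: 74 randomised 1:1 gives 74 / 2 = 37 patients in Arm 2. The table is descriptive, so sample size, alpha and the primary comparison are unaffected.

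**The case against.** The best defence is that the broad rules already require capture. Several sections ask for every event, Section 11.1 asks for significant laboratory findings, and one loosely worded sentence inside a definition should not be read as overriding them. Nor does that sentence say that other events will not be recorded. Much of this stands: loss of haematologic data is possible, not certain, and the two readings are not evenly balanced. It does not remove the conflict. Naming a grade and an exception has no function unless it narrows something, and the sentence covers recording as well as reporting.

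A reader might infer two stronger points.

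- **That the plan will lose haematologic toxicity.** The documents do not support this. Sections 11.1, 11.2.2 and 11.3 each provide a route for cytopenia to be captured, and severe infection is recorded under either rule.
- **That Section 14 is wrong not to compare blood counts between arms, since a CBC is scheduled in both arms at months 3, 6 and 12.** The documents do not support this either. The objective concerns the radiation arm only, and Section 10 deliberately excludes Arm 1 from adverse-event evaluation. Such a table would also be poorly timed. Regimens run from 1 to 10 fractions, no CBC is scheduled during radiation, and the first follow-up count is at month 3 (± 4 weeks). Telephone visits defer the count, counts after a skeletal event are optional, and Arm 1 may itself receive palliative radiation. A near-null result could falsely reassure.

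**Conclusion.** The point holds as a conflict between recording rules that is cheap to remove. If Section 11.2.1 is followed, cytopenia of any grade and all Grade 1–2 events are missing from an Arm 2 table that Section 14 describes as complete. If Sections 11.1 and 11.3 are followed, nothing is lost. How many events are at stake cannot be derived from the documents. The conclusion rests on reading the Section 11.2.1 sentence as a limit on recording, which is its natural sense but not its only possible one. It is a minor improvement to a secondary, descriptive safety summary. It does not bear on efficacy and does not show that a between-arm toxicity comparison is owed.

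**What to change.** Replace the sentence in Section 11.2.1 with wording such as:

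> In Arm 2, every adverse event after the first radiation dose will be graded by CTCAE and entered on the case report form. This includes haematologic toxicity of any grade, whether found on a scheduled or an unscheduled blood count. Where a Grade 3 threshold is used, it governs expedited reporting only and does not limit what is recorded.

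This restates what Sections 11.1, 11.3 and 14 already require, so those sections need no change. Two partial repairs should be avoided. Deleting only the haematologic exception leaves the grade threshold in conflict with the other sections. Taking haematologic toxicity from the scheduled counts alone would narrow capture to months 3, 6 and 12.

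Optionally, and not as a requirement, the counts already scheduled in both arms could be tabulated by arm at months 3, 6 and 12. The table should be descriptive only, give the number of patients with a count at each visit, and note that falls before month 3 are missed.

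**Cost.** One sentence, no new visits or tests, and slightly more abstraction. Some recorded cytopenias will be due to systemic therapy, which Section 5.2 leaves unrestricted. The attribution step in Section 11.2.4 ("attribution is the assessment of the likelihood that an adverse event is caused by the research agent, or protocol intervention") is the existing means of labelling them.
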